Given the inconsistent results conventional physical therapy has delivered in the treatment of lateral epicondylitis, and the results of BFR on strength increase, and pain decrease with exercise, it reasons that BFR may be a useful tool in the rehabilitation of chronic degenerative tendinopathies such as lateral epicondylitis. We believe it may be possible to decrease the elbow pain a patient feels while exercising with BFR, in order to increase their strength and function, and hopefully daily pain level in a manner that may be superior to conventional physical therapy.

Relevance to Sports Health Research

BFR devices are relatively new on the rehabilitation horizon, and as such, are purported to hold significant promise. We hope to begin a process of objective evaluation of the tools to see if they can be effective in treatment of traditionally difficult to treat degenerative tendinopathies.

Specific Aims

We wish to investigate whether BFR training is an effective tool in the rehabilitation of patients diagnosed with lateral epicondylitis. Low load BFR training has been shown to increase strength and hypertrophy in individuals with generalized muscle weakness and with lower extremity orthopedic ailments. Functional outcomes and pain are less reported in the literature and is worth investigating as increasing strength is a primary target in rehabilitation.

We propose to investigate the effectiveness of BFR in a population that represents the majority of patients seeking outpatient Physical Therapy services with a diagnosis of lateral epicondylitis.

We plan to achieve this project by addressing the following aims:

1. To evaluate if a BFR rehabilitation program results in superior self reported function and pain compared to a usual care group in the treatment of lateral epicondylitis.
 - a. This aim tests the hypothesis that lower resistance loading exercises when coupled with BFR will have positive effects on pain and overall function.
2. To determine if a BFR rehabilitation program results in increased grip strength compared to a usual care group in the treatment of lateral epicondylitis.
 - a. This aim tests the hypothesis that a patient who undergoes BFR rehabilitation with lower resistance load exercises, will demonstrate increases in objectively measured grip strength.

Outcomes

Primary Outcomes:

1. Change in Patient Rated Tennis Elbow Evaluation (PRTEE)²³ at 12 months from baseline.

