 - a. We will also collect this data at final in person therapy visit, 3 months, and 6 months from baseline. These will be considered secondary outcomes.

Secondary Outcomes:

1. Change in Numeric pain rating scale (NPRS) from baseline visit to 12 months.
2. Change in maximum pain free grip strength from baseline to final therapy visit.
3. Change in maximum grip strength from baseline to final therapy visit
4. We will provide descriptive statistics as to whether subjects have sought other treatment after finishing our treatment protocol. This data will be collected as part of the 3, 6, 12 month contacts.
 - a. Other treatments sought will include: further doctor's visits, oral medications prescribed, injection therapy (and what type), surgical treatment.

The NPRS and PRTEE are validated, standardized outcome measures commonly used when assessing lateral epicondylitis. Assessing grip strength is standard practice, however, we wished to differentiate between maximum grip strength vs pain limiting grip strength.

Long Term Goals

The long term goals depend somewhat on the outcome of the trial. If the new BFR device shows promise and is seen to be superior to standard therapy, there is potential to evaluate its use in multiple types of chronic degenerative tendinopathy. There is also the potential to decrease the number of patient visits to therapy offices, increasing the value of therapy if it is effective. We also see the potential to apply to other degenerative conditions such as osteoarthritis to see if there is potential to improve therapy techniques and benefits for conditions such as these.

Research Design and Methods

Brief Design Description

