Patients and treating therapists will be aware of the treatment rendered. Patients will self-enter their answers on the PRTEE and NPRS at the first, and 6th or final physical therapy visit. This data will either be self-entered to REDCap website, or onto paper copy which will be entered into REDCap by researcher blinded to their allocation. The treating physical therapists will be blinded to these results. Grip strength, and maximum pain free grip will be recorded at each therapy visit by treating physical therapist who is not blinded to the treatment allocation. We have made this decision understanding the risk of biasing a secondary outcome, but the burden of having multiple therapists at each site accommodate the institutional expectations for participating in research in order to have blinded assessment, has made this a necessity. Post treatment assessment with the NPRS and the PRTEE will be done via online REDCap survey. A researcher blinded to allocation will be responsible for contacting patients not responding to email contact to request completion of the online survey. A separate researcher, blinded to group allocation will analyze the final results that will be stored in REDCap.

Device

We will be using the Delfi personalized tourniquet system for BFR in this study (Delfi Medical Innovations Inc., [name]). The Delfi system allows a specific limb occlusion pressure to be applied to a patient's limb in order to reduce their arterial flow by a proscribed amount. In our project, we will use 50% occlusion as the standard ²².

Physical therapy staff participating in the study will be trained on the use of BFR technology. At least one therapist will attend formal training provided by the device developer prior to beginning enrollment in the study. After receiving training, all other participating therapists will be trained by the therapist/s who have received formal training.

Statement from the manufacturer (received via email):

The Delfi PTS Personalized Tourniquet System for BFR device when used according to the device's Intended Use and Indications for Use statements in the Operator and Maintenance Manual is cleared for market under Delfi Medical Innovations Inc.'s FDA Device Listing for Pneumatic Tourniquets E127474 as a Class I device exempt from premarket notification procedures. Delfi Medical Innovations Inc. is a registered establishment with the FDA under registration number 9681444.

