The study population proposed is readily accessible at Cleveland Clinic Akron General as a review specifically of Akron General Orthopedic practitioners over a 10 month period covering 2017-2018 showed over 200 office visits with the diagnosis code for lateral epicondylitis. Cleveland Clinic Akron General as a facility has the adequate resources available to support the study, including electronic medical records and REDCap. In addition, qualified and experienced medical staff members will conduct the study, including a sports medicine physician, two doctors of physical therapy with residency training in sports medicine, research coordinator/biostatistician, and a master's level athletic trainer. The authors will also apply for summer research interns as part of the annual Cleveland Clinic Akron General program. Co-investigators will be trained on the protocol and only IRRB approved staff will be conducting research related procedures.

Outcomes assessment

Numeric Pain Rating Scale (NPRS), Patient Rated Tennis Elbow Evaluation (PRTEE)

For the NPRS, subjects will be asked to rate their pain 0-10, with 0 being no pain and 10 being worst pain imaginable. Subjects will be asked to rate their least pain in the last 3 days and worst pain the last 3 days.

For the PRTEE, it will be issued in paper or electronic format to the patient prior to physical examination.

In both cases, the scales will be collected on the first/baseline visit, as well as at the final therapy visit (if known). They will then be collected electronically by email (with phone call reminders if necessary) at 3, 6, and 12 months.

Grip Strength Testing

The subject will be given a calibrated hand dynamometer and will be instructed to keep arm adducted and elbow bent to 90 degrees while in a sitting position. The subject will be asked to squeeze until onset of pain that is 2 points above resting pain on NPRS. There will be two attempts, with 60 seconds in between, and the average will be recorded. Then, using the same positioning, the subject will perform 2 max effort squeezes within their pain tolerance. The average of the two measure will be recorded as done previously.

Therapy Protocols

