program, and that the primary difference between treatments was high load standard exercise, and low load exercise with blood flow restriction.

Related to the above, is the lack of a placebo group. We would like to include a placebo group using a blood pressure cuff just minimally inflated, but this would have required increasing the recruitment of patients to 66, and we felt this was too daunting to be done as an early phase trial.

Our final concern is regarding blinding of the treating therapists to the grip strength testing. For efficiency reasons, we have decided to allow the treating therapists to be aware of the results of these tests (secondary outcomes), and to record them in the patient charts.

Our final concern is regarding blinding of the treating therapists to the grip strength testing. For efficiency reasons, we have decided to allow the treating therapists to be aware of the results of these tests (secondary outcomes), and to record them in the patient charts.

Plans for dissemination of findings

Upon completion of the study it is our intention to submit the research to a national/international level sports medicine or physical therapy conference. We also intend to submit a manuscript to a sports medicine or physical therapy journal.

References

2. Jayanthi N. Epicondylitis (tennis and golf elbow). UpToDate.com. [https://www.uptodate.com/contents/epicondylitis-tennis-and-golf-elbow?search=tennis elbow&source=search_result&selectedTitle=1~19&usage_type=default&display_rank=1](https://www.uptodate.com/contents/epicondylitis-tennis-and-golf-elbow?search=tennis%20elbow&source=search_result&selectedTitle=1~19&usage_type=default&display_rank=1). Accessed September 1, 2019.

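### Grip strength, the only measure behind Aim 2, is tested by the unblinded treating therapist, and the protocol states no control on encouragement or feedback during the test

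*Combined protocol and SAP*

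**What the plan says.** Specific Aims, item 2a, predicts that patients treated with BFR "will demonstrate increases in objectively measured grip strength". The Outcomes section lists two grip endpoints, both secondary: "Change in maximum pain free grip strength from baseline to final therapy visit" and "Change in maximum grip strength from baseline to final therapy visit".

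Grip Strength Testing fixes a calibrated dynamometer, the seated posture and elbow angle, two attempts per test and averaging. In the first test the patient squeezes until pain is 2 NPRS points above rest. In the second, "the subject will perform 2 max effort squeezes within their pain tolerance".

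On masking, the Blinding section states that "Patients and treating therapists will be aware of the treatment rendered" and that grip "will be recorded at each therapy visit by treating physical therapist who is not blinded to the treatment allocation". It adds "We have made this decision understanding the risk of biasing a secondary outcome" and gives the burden of a second therapist at each site as the reason. Potential Limitations of Study says, of grip testing, that "we have decided to allow the treating therapists to be aware of the results of these tests" and to chart them. Brief Design Description provides a 2-hour training session for one therapist per site, covering treatment delivery and data collection; Therapy Protocols adds study-specific training. Neither describes how grip testing is taught.

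**The concern.** A dynamometer reads force without judgement, but the force depends on how hard the patient tries and how much pain the patient accepts. Both can respond to what the tester says and to what the patient sees on the device. Here the tester delivers the treatment, knows the arm and may know earlier readings.

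If one arm is urged on more than the other, the difference enters the between-arm comparison directly. The analysis could not separate it from a real change in strength, and a larger sample would estimate the biased difference more precisely. One of the trial's two aims could then be reported as met, or as not met, because of how the test was run.

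**Working it through.** **No figure to reproduce.** The documents give no SD, target difference, power or sample size for grip. The check is a reading of the text, followed by an illustration.

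**Reading the sections together**

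| Possible source of influence | What the text provides |
|---|---|
| Instrument, posture, attempts, averaging | Fixed in Grip Strength Testing |
| Stop in the pain-limited test | Patient's own NPRS rise of 2 points |
| Wording of the instruction | Not stated |
| Encouragement during the squeeze | Not stated |
| Sight of the reading during the squeeze | Not stated |
| Access to earlier readings | Permitted (Potential Limitations of Study) |
| Identity of tester | Treating therapist, unblinded (Blinding) |
| Analysis addressing assessor influence | None in Statistical Analysis |

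By contrast, PRTEE and NPRS are self-entered, and the treating therapists are kept blind to those results (Blinding).

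The number of earlier readings is also unclear. Blinding has grip recorded at every visit, while the data-point list under Data Collection has it at entry and at the sixth or last visit. These need reconciling, because the first reading gives the therapist more earlier values to know.

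**Illustration: what a given shift would do**

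Inputs from the documents: two-sided alpha 0.05 (Statistical Analysis); 17 per group needed and 22 per group recruited (Power Analysis). The 17 was derived for PRTEE and serves here only as a plausible lower number with data. Assumption, not in the documents: prompting shifts the arm difference in grip change by b = 0.2, 0.3 or 0.5 SD, with no true effect.

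Method: two-sample t test on the change from baseline, with df = 2n − 2, noncentrality λ = b·√(n/2), and rejection probability P(|T| > t₀.₉₇₅), where T is noncentral t. Statistical Analysis plans repeated-measures ANOVA; with only two time points its group-by-time test is equivalent to this t test.

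- n = 17: df = 32, critical t = 2.037, √(17/2) = 2.915, so λ = 0.58, 0.87, 1.46.
- n = 22: df = 42, critical t = 2.018, √(22/2) = 3.317, so λ = 0.66, 0.99, 1.66.

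| Assumed shift b | 17 per arm | 22 per arm |
|---|---|---|
| 0 | 5.0% | 5.0% |
| 0.2 SD | 8.7% | 9.9% |
| 0.3 SD | 13.6% | 16.3% |
| 0.5 SD | 29.3% | 36.7% |

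Nearly all of the rejections fall in the direction of the shift: at 22 per arm, 9.5%, 16.2% and 36.7%. The rates are higher at 22 than at 17, so recruiting more patients makes a false finding from a fixed bias more likely.

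**The case against.** The strongest reply is that the protocol already says this. It names the tester as unblinded, accepts the risk, gives a reason and lists therapist knowledge of the results as a limitation. Grip is ranked secondary, and the primary PRTEE is self-entered and hidden from treating therapists. All of that stands, so a reader who inferred an undisclosed flaw, or a threat to the primary conclusion, would be wrong. But the staffing reason explains only the lack of a second assessor. A script and a no-encouragement rule need no second person, and disclosure does not reduce the bias.

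Second, the training may already cover prompting. Its content is not given, so the fair statement is that the protocol text states no control, not that none exists.

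Third, the wording of Aim 2a can simply contrast a dynamometer with the self-report measures of Aim 1. That is a natural reading, and the phrase does not claim blinded assessment. Clarifying it is mainly editorial.

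Fourth, a reader might infer that encouragement will favour BFR. The documents do not show this. Both arms receive supervised active treatment, nothing indicates that prompting would differ between them, and the shifts above have no source in the protocol.

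Fifth, a reader might infer that grip readings can be withheld freely because no exercise load depends on them. The documents do not establish that. Therapy Protocols sets the control arm's putty resistance by therapist assessment and does not say whether that draws on grip readings. Any change should therefore leave the values available after the test.

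**Conclusion.** The point holds as a low-to-moderate priority improvement. The only measure behind Aim 2 depends on effort and pain, its tester is unblinded, and the protocol text sets no rule on encouragement or feedback during testing. If prompting differed by arm it would appear as a strength difference in either direction. Whether it would differ, and by how much, cannot be learned from the documents. The range of about 9–29% at 17 per arm and 10–37% at 22 per arm rests wholly on the assumed 0.2–0.5 SD shift and on a simple t test of change. It shows sensitivity to such a bias and does not estimate it.

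**What to change.** In Grip Strength Testing, add:

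- One fixed instruction script, read word for word in both arms at every test, with no encouragement or feedback during the squeeze.
- Where the dynamometer allows, the reading kept out of view of patient and therapist until release. The protocol does not say whether the device holds its peak reading, so this must be conditional.
- The value entered in REDCap before earlier values are consulted. It may be charted afterwards as now.

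In Specific Aims, item 2a, describe grip as dynamometer-measured by the unblinded treating therapist, and interpret Aim 2 with that limitation. Reconcile the two statements of when grip is recorded.

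The cost is one page of test instructions and a small change in data-entry order, with no added staff or visits. The therapist does not see the trend while testing. Some bias would remain: the same therapist may remember earlier values, and patients who know their arm may differ in effort or pain tolerance through expectation.

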Blood Restriction Training (BFR) is an innovative procedure that involves measuring the Limb Occlusive Pressure, and then setting a tourniquet to a set percentage to restrict blood flow to the exercising body region⁴. It is hypothesized the combination of hypoxia and tension results in metabolic stress and activation of several pathways to increase strength and hypertrophy⁵⁻⁷. Most of the mechanisms are theoretical, but include elevating systemic hormone levels, production of reactive oxygen species (ROS), intramuscular anabolic/anti-catabolic signaling, and increased fast-twitch fiber recruitment.^{4,6-10}. Although the mechanisms are unclear, there is mounting clinical evidence supporting the increase in strength and hypertrophy ^{5,8,9,11-13}. The effect of BFR on pain does show promise when treating knee pathology. BFR has been shown to improve strength, and in some cases pain during exercise as well as or better than conventional therapy in patients with osteoarthritis ¹⁴, and in post-operative patients ^{15,16}. The effect of BFR on pain and function is less clear, and current evidence exists only in knee pathology ¹⁴⁻¹⁸. A 2017 systematic review examining the effect of BFR on musculoskeletal conditions found moderate effect on increasing strength. It appears BFR is not superior to heavy load resistance training, but in the injured population it is not always possible to perform heavy load training ¹⁹.

Regarding safety, there is a very low incidence of side effects with BFR. Wernbom et al⁵ performed a review of the safety reports in 13 BFR specific studies, and the only reported side effects were muscle pain related to the exercise, and some level of endothelial dysfunction related to acute bouts of exercise which resolved within 60 minutes. Nakajima et al²⁰ report on a Japanese survey of KAATSU training (a method very similar to BFR), and report venous thrombosis (0.055%), pulmonary embolism (0.008%), rhabdomyolysis (0.008%). The authors concluded that BFR training is a safe intervention.

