This will be a randomized, controlled, open label trial. A total of 44 subjects will be recruited. Each group will be divided equally with 22 subjects having been diagnosed with lateral elbow pain. Subjects will be recruited from CCAG physicians located within the CCAG health system, as well as at physical therapy locations at Health and Wellness Centers in Bath, Green, and Stow. A team of physical and occupational therapists have been recruited including therapists and athletic trainers who are present at each office. At each site, 1 therapist will undergo a 2 hour standardized training session on delivery of treatment and data collection. Patients evaluated and found to have the appropriate criteria by either physicians or physical therapists will be given a research information sheet (see appendix) offering the opportunity to participate in a research study at the above mentioned locations. The patients interested will be consented by phone, or in person once they present to physical therapy office.

Timeline of Study

The goal is a 6-week treatment period at 1 PT visit per week. In ideal situation the visits occur in consecutive weeks, but will be considered per protocol with 6 visits over a 12 week period. Follow up will occur for 12 months after the initial therapy visit. We anticipate the total open period of time to last between 2-3 years for completion of 1 year follow up, 2019-2022.

- A patient can elect to drop from the study at any time.
- A patient's treatment will be considered completed if they cannot attend 6 visits within the 12 week time frame.
- A patient can be discharged from care prior to 6 weeks if all clinical goals set at the initial therapy assessment are met. If this occurs the outcomes measures expected at the 6th visit will be recorded at this visit and considered equivalent to the 6th visit outcomes.

Recruitment/Enrollment

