Once patients have consented to participation, subjects will be randomly assigned to either intervention or control group-both consisting of 22 patients. Consent will be obtained by referring physicians, or physical therapists at approved sites participating in the study [further details regarding consent procedure below]. At all physical therapy sites participating in the study, patient service representatives will be trained in the study recruitment, collecting patient enrollment paperwork and other clerical needs. Allocation will occur in blocks of 4 by opaque envelope. The envelopes will be generated by web based randomization software²¹ placed into opaque, sequentially numbered envelopes and delivered to participating physical therapy clinics prior to beginning recruitment. Two sites will contain 4 blocks of 4 envelopes, and one site will contain 3 blocks of 4, ensuring a total of 44 patients. If one site or another enrolls more patients, only a full block of 4 envelopes will be transferred to that site for further enrollment. The envelopes will be stored in the desk of the directing physical therapist at each location,

and only removed once a patient has been enrolled. Once patients consent to enroll in the study, they will receive the next envelope in sequence in the group of 4, and be allocated to either the intervention or control group. The envelope will contain a number which the treating physical therapist will then compare to the master allocation list, which will reveal which treatment group #1 or #2(intervention or control) the patient has been allocated; it will also contain the patient's assigned identification number (PID). The treating physical therapist will be responsible for communicating the subject's allocation and PID which will be contained in their envelope to the primary investigator, who will hold the confidential master list. Outcomes data will be collected in a separately in REDCap.

Blinding

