Inclusion / Exclusion Criteria:

Included

The diagnoses included are lateral elbow pain, lateral epicondylitis, or lateral epicondylalgia, more general diagnoses elbow tendinitis or elbow pain will be included if their clinical picture at physical therapy meets criteria for lateral epicondylitis. If the inclusion diagnosis is other than lateral epicondylitis or tennis elbow, we will confirm the diagnosis at the first therapy visit with tenderness at the lateral epicondyle and/or pain with resisted wrist/long finger extension at the lateral epicondyle. All participants must be between the age of 18 and 70 years old and have had pain for 4 weeks or more.

Excluded

Patients presenting with a ligamentous elbow sprain, osteoarthritis of elbow and cervical radiculopathy in the affected limb will be excluded from the study. Other exclusion criteria would be inability to consent, any history of ligamentous, bony or other soft tissue reconstruction surgery at the affected elbow, history of DVT, history of endothelial dysfunction, peripheral vascular disease, pregnancy, surgical procedure on their contralateral extremity, active infection, injection therapy (corticosteroid, platelet rich plasma, or other injection therapy) in the prior 3 months to the affected site, and cancer; any surgery on affected arm in last 1 year; current fracture in affected arm; history of crush injury to affected arm; history of lymphectomy (such as axillary exploration with breast surgery, lymph node biopsy in the affected axilla/arm), sickle cell anemia or trait; kidney dialysis; history of syncope/passing out with pressure to body (such as massage, or blood pressure cuff).

Assessment of Resources:

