Once randomized, Twenty-two subjects will be placed into a control group, in which standard loading of the wrist and finger extensors using 70% of 1 Rep max (RM), determined using a 1 RM calculator, will be given as well strengthening pronators, supinators and grip strength. The experimental group of 22 will receive blood flow restricted wrist extensor strengthening at 50% limb occlusion using 20% of their 1 RM. To assess 20% of 1 RM of the extensors, a weight will be given to the patient to see how many repetitions can be performed. The weight and number of reps will be entered into a 1 RM calculator so that 20% of the 1 RM can be determined. Strengthening using BFR will occur once per week in clinic, in addition to standard strengthening of supinator, pronators and grip strength. They will also perform the same standardized home exercise program as the control group. All participants will receive the same instruments at baseline and 6th visit. Treatment performed at the three participating clinics will undergo standardized training in the use of BFR strengthening as well as specific study protocol training prior to the onset of the study.

The subjects placed into the control group will receive standard loading of the wrist and finger extensors using 70% of 1 Rep max (RM). The subject will be given the appropriate weight in clinic to be able to do 3 sets of 15. The subject will also strengthen pronators, supinators using a weighted stick to a 7 out of 10 on a rate of perceived exertion (RPE) scale. Grip strength will be addressed using therapeutic putty, resistance determined by the therapist's assessment, having the patient perform 3 sets of 2 min of squeezing the putty. The therapist will have discretion on if cervical spine, thoracic spine or shoulder treatment is warranted, based on standard practice. This treatment will occur for 6 visits in the clinic.

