BFR training has been shown to be safe and can also be applied to persons with various kinds of physical condition including cerebrovascular diseases, orthopedic diseases, obesity, cardiac diseases, neuromuscular diseases, diabetes, hypertension, and respiratory diseases. Nakajima performed a national survey of over 12,000 patients and found that the number of severe side effects is very low. The most frequent side effect is subcutaneous hemorrhage that is transient. Several papers showed that BFR training combined with low-intensity exercise does not cause severe muscle injury, and there is no elevation of creatine phosphokinase (CPK)²⁶ or rhabdomyolysis, as compared with heavy exercises.

Risks include primarily the risk of failure of physical therapy. As we know that therapy has variable responses with this condition, the possibility that the patient does not respond well to either control, or intervention treatment is real.

Medical risks appear very unlikely, with no significant side effects beyond muscle pain reported with BFR in the past.

KAATSU training, which is a Japanese version of blood flow occlusion training, has shown risks of major side effects to be less than 0.1% on a national survey of those using it. These risks included venous thrombo-embolism and rhabdomyolysis.

We believe significant side effects are very unlikely based on published data, and the idea that a trained therapist will be supervising the treatment of our patients.

We cannot envision any significant risk beyond muscle soreness, and possibly skin bruising for patients who have been enrolled in the intervention arm.

Serious Adverse events

Any significant adverse event-such as a venous thrombo-embolism, or significant medical event occurring within 48 hours of treatment will be recorded and reported.

If any significant similar medical event (such as a pulmonary embolism, angina episode, etc.) occurs in patients in any way which indicates a pattern of risk in the intervention group, the investigators will meet to discuss discontinuation of the trial.

Compensation for Injuries

No compensation for injury is planned. Subjects will be informed at the time of consent that any adverse event will be treated and covered as usual by the patient and their health insurance.

Benefits to Subjects

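### The clot-history exclusion names only DVT, so a patient with a past pulmonary embolism and no recorded DVT is eligible for the tourniquet arm

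*Combined protocol and SAP*

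**What the plan says.** The Excluded paragraph of Inclusion / Exclusion Criteria gives a long and fairly specific list. Its vascular items, apart from sickle cell disease or trait, are in the run "history of DVT, history of endothelial dysfunction, peripheral vascular disease, pregnancy". Nothing else in the list refers to a previous clot, a clotting disorder or anticoagulant treatment, and the list does not end with a general clause leaving other cases to the investigator's judgement.

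The exposure is set out in Therapy Protocols: "The experimental group of 22 will receive blood flow restricted wrist extensor strengthening at 50% limb occlusion", delivered by a tourniquet on the upper arm.

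Elsewhere the protocol treats clots as a hazard of this kind of training:

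- The safety paragraph of the background cites a survey of KAATSU, which it regards as close to BFR, with rates of 0.055% for venous thrombosis and 0.008% for pulmonary embolism.
- Serious Adverse events requires recording and reporting of "Any significant adverse event-such as a venous thrombo-embolism, or significant medical event occurring within 48 hours of treatment". It also gives pulmonary embolism as an example of an event that, if it showed a pattern of risk in the intervention group, would bring the investigators together to discuss stopping.
- Risks and Side Effects keeps this in proportion: "We believe significant side effects are very unlikely based on published data".

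On the route into the trial, Brief Design Description says "Patients evaluated and found to have the appropriate criteria by either physicians or physical therapists will be given a research information sheet", and Randomization/Allocation says "Once patients consent to enroll in the study, they will receive the next envelope in sequence".

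**The concern.** The sponsor decided that a past DVT should keep a patient away from the cuff. A past pulmonary embolism is the related form of the same disease, and Serious Adverse events uses the joint term venous thrombo-embolism for the adverse event. The documents give no reason to exclude one form and admit the other, so an omission in drafting seems likelier than a deliberate choice.

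What is at stake is patient safety in a rare case. A patient whose record shows a pulmonary embolism, with no DVT found, passes the written list and, with 22 patients in each group, has an even chance of the tourniquet arm. The sample size, power, primary analysis and interpretation do not depend on this point.

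**Working it through.** The plan states no figure on this point, so there is none to reproduce. The check has two parts.

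**Reading the criteria against a test case.** Take a patient with a past pulmonary embolism, no recorded DVT, and otherwise eligible.

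1. The DVT item, read literally, does not apply.
2. The neighbouring items, endothelial dysfunction and peripheral vascular disease, do not plainly cover a clot in the lung.
3. The remaining items (among them previous surgery, fracture, crush injury, lymph node procedures, sickle cell disease or trait, dialysis, cancer, and syncope under pressure) do not apply.
4. There is no discretion clause to fall back on.
5. Data Collection lists active and past medical history and current medications as baseline items, collected after consent. No rule turns a past pulmonary embolism found there into an exclusion, and the order of this collection relative to the envelope is not stated.

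The patient is therefore eligible as the plan is written.

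**Size of the exposure.** The number of cuff patients is n = 22 (Therapy Protocols) and the total is 44. The proportion p of otherwise eligible patients with a past pulmonary embolism and no recorded DVT is not in the documents. I assume a range of 0.1% to 1%, with patients independent and the list applied literally.

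| Quantity | Formula | p = 0.001 | p = 0.01 |
|---|---|---|---|
| Expected exposed to the cuff | 22 × p | 0.022 | 0.22 |
| Chance that at least one is exposed | 1 − (1 − p)^22 | 1 − 0.999^22 = 2.2% | 1 − 0.99^22 = 19.8% |
| Recruits lost if the item is widened | 44 × p | 0.044 | 0.44 |

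**What cannot be computed.** At the cited survey rates, 22 cuff patients give 22 × 0.00055 = 0.012 expected venous thromboses (1.2% chance of at least one) and 22 × 0.00008 = 0.0018 expected pulmonary emboli (0.18% chance of at least one). These rates describe survey users in general. They say nothing about people with a previous clot, so they cannot be used for harm per exposed patient.

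**The case against.** The strongest reply is that this is an optional wording suggestion. No part of the protocol discusses a past pulmonary embolism as a risk factor. Naming a hazard does not by itself call for a history exclusion: angina and rhabdomyolysis are also named, and a history of either is not excluded. Many of the neighbouring exclusions concern the limb or its vessels, so an exclusion confined to limb veins could be deliberate. A clinician may well take a DVT history to include a clot that travelled to the lung. Medical history and medications are recorded at baseline, and a trained therapist supervises the sessions. The device manual, training content, consent form and information sheet may screen for clotting history, and none of them can be seen here. The prevalence range has no anchor in the documents, and the 20% comes entirely from its upper end. Finally, clotting disorders and anticoagulant use are missing too, so adding only pulmonary embolism is selective.

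Much of this stands. The relevance of a past pulmonary embolism is inferred from the sponsor's choice to exclude past DVT, the range is an assumption, and the unseen documents may help. What does not stand is that any of this closes the gap in the written rule. The DVT item is not limited to the affected arm, which weakens the limb-vein reading. The background lists venous thrombosis and pulmonary embolism separately, which weakens the reading that one term covers both. The argument does not need every named hazard to have a history exclusion; it is only that a disease already excluded in one form was left in under its other. Whether to go further, to clotting disorders or anticoagulants, is a separate clinical decision for the sponsor.

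**Conclusion.** The concern holds as a minor gap in safety wording. Read literally, the list admits a patient with a past pulmonary embolism and no recorded DVT to a trial in which half the patients exercise under a tourniquet.

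That the list omits this history is established by the text. That the omission matters clinically is an inference from the sponsor's own DVT exclusion and the plan's use of venous thrombo-embolism as a single category. The expected number exposed is well below one patient across the whole assumed range, and the probability of harm to such a patient cannot be estimated from the documents. The case for acting is that the correction costs almost nothing. Confidence is medium, because the unseen training and consent material may already screen for this.

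**What to change.** Under Inclusion / Exclusion Criteria, replace the DVT item with *history of venous thrombo-embolism (DVT or pulmonary embolism)*. Add one screening question on past clots when eligibility is assessed, and require the answer before the allocation envelope is given. Relying on the baseline history form is not enough, since it is completed after consent and is not tied to eligibility.

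The cost is a one-phrase amendment, one question, and at most an occasional lost recruit. Nothing in the randomisation, sample size or analysis needs to change.
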